Power Analysis. Previous research¹⁰⁷ suggests that an intervention that is similar to BBTF could produce an improvement in father engagement ($d = .42$).¹⁰⁸ Assuming an effect size of $d = .42$, a one-tailed alpha of .05, and a sample size of 144 participants (72 per group), we obtained a power of .80 for this design. Assuming a 20% dropout rate, the total sample needs to be 180 participants, 90 per group.

Sample Recruitment. Three recruiters, ethnically matched to the participants and with ties to the community, were trained in minority outreach by the research team to establish relationships with fathers that supported recruitment. They were also trained to give presentations about the program to community groups. It was essential that the data collectors hired were comfortable in low-income communities, highly personable, and very patient (particularly when parents failed to show up for appointments). All program advertisements included a brief description of a self-improvement program for AA fathers, featured photographs of scenes of fathers meeting together, and provided a number to call and e-mail address for further information. We continued with the highly successful active (recruiters meet directly with potential participants) and passive (potential participants are prompted to contact the staff) recruitment strategies used in our extensive prior work in low-income Chicago communities.^{95,104,105} Recruiters met with key informants already identified from churches, barbershops, community centers, schools, day care centers, local business establishments, dry cleaners, and sports venues to obtain the anticipated broad reach. Key informants were given brochures/flyers to pass on the information to potential participants. In addition, notices were placed in church bulletins and community newspapers. Active strategies included giving presentations at community churches and other community gathering places.

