Data Analysis Data analysis is described with respect to the three specific aims and hypotheses that were tested. Missing data was imputed using SAS Proc MI, a multiple imputation computer program based on the work of Rubin.¹³¹ All continuous data was examined for statistical normality. Histograms were obtained for these variables, and skew and kurtosis were assessed in order to assess statistical normality. Where possible, we normalized these data using Tukey's ladder of transformation¹³² before conducting statistical analysis. SPSS for Windows (Version 11) and SAS (Version 9.1) was used for data management and statistical analysis. A two-tailed 0.05 significance level was used for all statistical tests except where noted below. All analyses were performed on an intent-to-treat basis. Outcome measures that could be successfully transformed to achieve normality were in all likelihood close enough to a normal distribution that the robust nature of the F-test made it possible to obtain reasonable p values in the study.

Descriptive statistics on the sample data for all research variables were obtained. In addition, one-way ANOVAs and chi-square analysis on the demographic and baseline research measures were performed between the intervention and control groups to determine that they

were comparable. The effects of participant attrition on the research variable were also assessed using one-way ANOVAs.

Hypothesis 1: Relative to the attention control condition, BBTF program fathers will report better father outcomes (psychological well-being, parenting competence, and father-mother relationship quality) and greater paternal involvement (material support, in-kind support, father-child interaction) at 12 weeks and 24 weeks.

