Data analysis were a repeated measures analysis of variance (RM-ANOVA) to address Hypothesis 1. The basic design for these analyses was a 2x3 design with three assessment time points (the within-subjects factor) crossed with the two treatment conditions (BBTF and the comparison group [the between-subjects factor]). The null hypothesis for all these analyses was that changes for all dependent measures (psychological well-being, parenting competence, father-mother relationship quality, material support, in-kind support, and father-child interaction) would remain constant for the two groups over time. The alternative hypothesis was that they would increase over time in the BBTF group relative to the control group. This was the interaction effect in the RM-ANOVA. An initial multivariate analysis was be conducted first to see if there was any overall effect. If the null hypothesis was rejected in the multivariate analysis, we examined the univariate analyses. We tested for violations of sphericity, and if they were in evidence, then a Greenhouse-Geisser correction was used to estimate probability values.

In order to determine when these changes occurred across the three assessment time points, a follow-up analysis was conducted with time reparameterized into a set of two orthogonal Helmert contrasts. The two contrasts were of the form (1, -1/2, -1/2; 0, 1, -1), where if the first contrast was significant, this indicated that the critical differences occurred between times 1 and 2; and if the second was significant, the changes took place between times 2 and 3. This informed us as to the transition point or points where the velocity changes were greatest between the treatment and comparison groups.

Hypothesis 2: Across both conditions, father outcomes and post-intervention ratings of father-mother relationship quality will mediate paternal involvement at 12 weeks and 24 weeks.

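### The stated power of .80 uses a one-tailed alpha of .05, but the analysis plan tests at two-tailed .05; the same calculation then gives .71, and power for the planned interaction test is not given.

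*Combined protocol and SAP*

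**What the plan says.** The Power Analysis paragraph takes from earlier research that a similar intervention "could produce an improvement in father engagement ($d = .42"). It then states "a one-tailed alpha of .05, and a sample size of 144 participants (72 per group), we obtained a power of .80 for this design", and inflates 144 to 180 (90 per group) for 20% dropout. No other justification of the sample size is given.

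The Data Analysis section sets the significance level: "A two-tailed 0.05 significance level was used for all statistical tests except where noted below". It also states "All analyses were performed on an intent-to-treat basis" and "Missing data was imputed using SAS Proc MI".

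Under Hypothesis 1 the test is described as follows: "The basic design for these analyses was a 2x3 design with three assessment time points", crossed with two conditions. The alternative is that outcomes rise over time under BBTF relative to control, and "This was the interaction effect in the RM-ANOVA". A multivariate test comes first, and the univariate tests follow only if it rejects. Hypothesis 3a uses the same analysis; Hypotheses 2 and 3b use regression-based mediation. None of these descriptions names a one-tailed test or another alpha.

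**The concern.** The sample size was set under one error rate and the tests are declared under another. A one-tailed test at .05 uses a lower critical value than a two-tailed test at .05, so power computed for the first overstates power for the second.

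There is also a mismatch of test. The plan says the .80 applies to this design, but its inputs (d, alpha and n per group) are those of a two-group comparison at one time point. The design is a two-group, three-occasion study analysed through an interaction. The power of that test also depends on the correlation between a father's repeated scores and on how large the effect is at 12 and at 24 weeks. None of these is stated.

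The 144 completers and 180 enrolled fathers rest on this one figure. A reader faced with a non-significant interaction would judge it against 80% power at two-tailed .05, which the calculation does not show.

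**Working it through.** **Inputs from the document.** d = .42, one-tailed alpha .05, 72 per group, power .80, 20% dropout and 180 enrolled (Power Analysis); 1:1 allocation (Overall Study Design); two-tailed .05 (Data Analysis); 2x3 design with the interaction as the test (Hypothesis 1).

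**Step 1: reproduce the plan's figure.** Two-sample t test with n per group, noncentrality d × √(n/2), df = 2n − 2. For n = 72 the noncentrality is .42 × √36 = 2.52, with df = 142.
- One-tailed .05: power .806 (normal approximation .809). This matches the stated .80.
- Dropout: 144 / (1 − .20) = 180. This also matches.

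**Step 2: change only the sidedness.**
- Two-tailed .05, 72 per group: power .706 (normal approximation .712). The chance of missing d = .42 rises from about 19% to about 29%.
- Effect detectable with .80 power, two-tailed, 72 per group: d = .47.
- Two-tailed .80 at d = .42: 89 per group gives .796 and 90 gives .800. Ninety completers per group is all 180 enrolled fathers. With the plan's 20% dropout, 180 completers would need 180 / .80 = 225 enrolled.

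**Step 3: look for an exception.** After the two-tailed rule, the text covers Hypotheses 1, 2, 3a and 3b. The alternative under Hypothesis 1 is worded directionally, but no one-tailed level is set. With three occasions and two groups the interaction has (3 − 1) × (2 − 1) = 2 numerator df, and an F test on 2 df has no one-tailed form.

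**Step 4: what the planned test might give.** The following are assumptions, not taken from the document: compound symmetry with within-person correlation ρ, no group difference at baseline, one outcome, and complete data. Let e be the group differences in SD units at baseline, 12 and 24 weeks. The test is F on 2 and 2(2n − 2) df, with noncentrality (n/2) × Σ(e − ē)² / (1 − ρ).

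For e = (0, .42, .42), ē = .28 and Σ(e − ē)² = .0784 + .0196 + .0196 = .1176. With n = 72 and ρ = .5 the noncentrality is 36 × .1176 / .5 = 8.47 and power is .74. For an effect of .21 at one follow-up and .42 at the other, the sum is .0882.

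| Effect at the two follow-ups | n per group | ρ = .3 | ρ = .5 | ρ = .6 | ρ = .7 | ρ at which power is .80 |
|---|---|---|---|---|---|---|
| .42 and .42 | 72 | .58 | .74 | .83 | .93 | about .57 |
| .42 and .42 | 90 | .69 | .84 | .91 | .97 | about .46 |
| .21 and .42 (either order) | 72 | .46 | .61 | .71 | .83 | about .67 |

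A simulation of the first row (4000 runs per cell) gave .59, .73, .84 and .93.

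**The case against.** The best defence is that .71 is not the power of any planned test. No two-group t test at one time point is planned, and repeated measures may recover what the two-tailed level loses: with 72 per group and the full effect at both follow-ups, the interaction reaches .80 at a correlation of about .57. This stands as a limit on the claim. It does not rescue the stated .80, because the plan gives no correlation and no pattern of effect.

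A second defence is that the directional alternative under Hypothesis 1 is the exception allowed for, and that the follow-up Helmert contrasts, with 1 df each, could be tested one-tailed. But a direction of expectation is not a significance level, and the contrasts only follow up the interaction test.

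A third is that imputation with intention-to-treat uses all 180 fathers. At best this lifts the two-group figure to .80, and only if every father contributes full information, which imputation does not in general restore. The plan itself bases power on 144.

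Some objections cut the other way. The block scheme in Overall Study Design (6 waves × 6 blocks × 4 fathers) yields 144 randomised, not 180. If 20% of those dropped out, about 58 per group would remain and two-group, two-tailed power would be about .61. The calculations here also leave out clustering of fathers within group cohorts and the multivariate test that precedes the univariate ones. These are separate matters, but they mean that .71 to .80 is not a firm range for the trial's power.

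Finally, the plan's arithmetic is right on its own inputs, type I error is unaffected, and the text is mostly in the past tense, so a restated figure cannot change the sample. That limits the consequence to how the results are read.

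**Conclusion.** The concern holds. The power figure and the analysis plan use different error rates, and nothing in the plan reconciles them. On the plan's own inputs, moving from one-tailed to two-tailed .05 takes a two-group comparison at one time point from .81 to .71 with 144 completers; .80 is reached only if all 180 fathers have complete data. These figures rest on d = .42 and independent observations.

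For the test actually planned, power cannot be derived from the document. The illustrative values of .46 to .93 with 72 per group depend on the assumed correlation (.3 to .7), compound symmetry and the assumed effect at each follow-up. They show that the planned test could lie on either side of .80. The conclusion is that .80 is unsupported at the declared alpha, not that the trial is shown to be underpowered. It should be fixed.

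**What to change.** Make the Power Analysis paragraph and the Data Analysis section agree, and restate power at two-tailed .05. Preferably give power for the condition-by-time interaction, stating the assumed within-person correlation and the assumed effects at 12 and 24 weeks, with a short range over both. If that is not done, report about .71 with 144 completers (detectable d about .47), labelled plainly as a two-group comparison at one time point and not as the power of the repeated measures ANOVA.

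The cost is a few sentences and one short calculation. No fathers or data are added, and the tests and their order stay as they are. The only drawback is that the restated figure may be less favourable than .80.

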COVER PAGE

The Dedicated African American Dad Study

NCT number-NCT02412748

Document date- July 15, 2016

Study Protocol & Statistical Analysis Plan

Overall Study Design

The study was a randomized clinical trial comparing the effects of a 12-week, 9-session fatherhood intervention, Building Bridges To Fatherhood (BBTF), to an attention control Financial Literacy Program (FLP) for AA non-resident fathers. Both conditions had a booster session at 18 weeks. At the booster session, the BBTF intervention group met to problem-solve around remaining challenges to positive father involvement and to refresh the content offered during the 12-week program. The attention control FLP condition met to discuss progress towards acquiring financial literacy, but without mention of fatherhood or father involvement. AA non-resident fathers were randomly assigned to the two conditions. This study used a block randomization procedure to facilitate equitable distribution of fathers into the BBTF and FLP conditions. Data collection began in study year 2 and continued for 2 years. During each wave's 12 weeks of recruitment, there were six blocks with four participants in each block. Each block was constructed with an equal number of BBTF and FLP assignments. Data collection was done at baseline, immediately post intervention (12 weeks), and 3 months post intervention (24 weeks).

The BBTF sessions and FLP control sessions were held at community colleges or community neighborhood sites. The study was conducted in a series of 6 waves over 96 weeks, alternating from westside sites southside sites over 96 weeks. Each wave began with 12 weeks of recruitment at community locations in proximity to the site. After the intervention and control groups had been recruited at each site, the two conditions began in parallel. The BBTF intervention and FLP control groups met on different nights and in different locations at the facility in order to minimize contamination. Once the groups began at one site, recruitment began for the next wave that was to be conducted at the alternate site. This design minimized historical contamination within a site because of the 12-week hiatus between the beginning of one series of groups and the end of the previous groups.

Subjects and Setting

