Fathers who meet inclusion criteria were informed that half of the fathers in the study would be randomly chosen to participate in the intervention group or the control group. Fathers had to agree to this procedure. After informed consent was obtained and baseline measures were completed, randomization took place. Block randomization assignments were kept in sealed envelopes in the research office in the order in which they were generated and then communicated by the project director to the data collector via text message, who was blind to the assignment prior to consenting and enrollment. The intervention and control groups began simultaneously at the end of the 12-week recruitment period.

Sample Retention. We continued with the successful strategies that resulted in 80% retention in prior community-based studies.^{47,106} First, the sessions were offered at two sites convenient to public transportation and with free parking. Participants were reimbursed for the cost of public transportation for coming to and from the study sites for the sessions and data collections (round-trip public transit card or \$10 gas card). They received a \$40 gift card after completing each of the three data collections. At the sessions, they were given a healthy drink and snack. Three times during the BBTF program (Weeks 4, 8, and 12), there were no scheduled session. To enhance fathers' opportunities for spending time with their child and serve as a motivator for continued involvement in the BBTF program, they were given a \$30.00 activity voucher for these weeks. Our prior work with fathers suggested that this was a retention strategy that was highly valued by AA fathers who were often seeking opportunities and resources for spending fun, engaging, and educational time with their children.^{9,47,109} We identified multiple means of remaining in contact with fathers including: work, home, and cell phone numbers; noted if they accepted text messages; home and e-mail addresses; and the contact information of three friends, relatives, or coworkers who would know how contact them should their phone service be terminated or mailing address change. Fathers received two reminder telephone calls, text messages, or e-mails two days prior to and the day of each group session and data collection. Fathers were given the opportunity to have the baseline, 12- and 24-week data collections either at the community college or another location of their choosing, such as their homes.

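### Fixed blocks of four, with assignments texted to the data collector, leave allocation concealment vulnerable, and masking of follow-up collectors is not described

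*Combined protocol and SAP*

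**What the plan says.** The allocation method is split between two sections of the combined protocol and SAP.

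- **Overall Study Design** gives the block structure: "During each wave's 12 weeks of recruitment, there were six blocks with four participants in each block". It adds: "Each block was constructed with an equal number of BBTF and FLP assignments". It also says: "The study was conducted in a series of 6 waves over 96 weeks".
- **Sample Recruitment** gives the handling of the list: "Block randomization assignments were kept in sealed envelopes in the research office in the order in which they were generated". On timing: "After informed consent was obtained and baseline measures were completed, randomization took place". On disclosure, assignments were "communicated by the project director to the data collector via text message, who was blind to the assignment prior to consenting and enrollment". On the start of treatment: "The intervention and control groups began simultaneously at the end of the 12-week recruitment period".

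Sample Retention lets fathers give their data at the college or at a place of their choice, such as home, and lets mothers answer by phone, by post or online. Procedures calls both parents' baseline instruments questionnaires. No section says who collects the 12- and 24-week data or whether those people know the arm.

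**The concern.** Sealed envelopes held centrally keep the next assignment from being read. They do not keep it from being worked out. In a 2:2 block of four, the assignments already made limit what can follow, and the fourth is always fixed by the first three. Someone who learns each assignment as it is made, and who also helps to enrol the next father, may be able to anticipate the next arm. The stated blindness of the data collector ends at enrolment, so it does not cover this.

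Two things are at stake.

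- **Selection.** Entry leaves room for discretion: one criterion turns on whether the mother is amenable to helping the father see the child, and consent meetings are arranged at the father's convenience. Foreknowledge could influence who is enrolled and in what order.
- **Outcome assessment.** Hypothesis 1 rests on what fathers report. If the texted collector also takes follow-up measures in person or by phone, knowledge of the arm could affect the answers.

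**Working it through.** **Figures in the plan.** The plan gives no figure for predictability. Its block counts multiply out as 6 blocks × 4 = 24 assignments per wave, and 24 × 6 waves = 144 in all. The Power Analysis asks for 180 recruited; the percentages below do not depend on which total applies.

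**Inputs**
- Block size 4, two per arm, fixed (Overall Study Design).
- Assignments used in generated order and disclosed to the data collector (Sample Recruitment).
- Number of collectors: not stated. Sample Recruitment uses both the plural and the singular. Assumed range: 1 to 3.
- Assumed: collectors know the block size and the position in the block, and release is father by father.

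**One collector who sees every assignment.** The six orders of a 2:2 block are equally likely. The best guess is the arm with more places left.

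| Position in block | Known with certainty | Guessed correctly |
|---|---|---|
| 1 | 0 | 1/2 |
| 2 | 0 | 2/3 |
| 3 | 1/3 (first two the same) | 2/3 |
| 4 | 1 | 1 |

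- Certain: (0 + 0 + 1/3 + 1)/4 = 1/3, or 33.3%. That is 8 of 24 per wave and 48 of 144.
- Correct guesses: (1/2 + 2/3 + 2/3 + 1)/4 = 17/24 = 70.8%.

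**k collectors who do not share information.** A given collector sees each previous assignment in the block with probability p = 1/k.

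- Certain at position 3: both previous ones seen and equal, p²/3.
- Certain at position 4: all three seen, p³, or exactly two seen and equal, 3p²(1−p)/3. The sum is p².
- Average over the block: (p²/3 + p²)/4 = p²/3.
- Correct guesses by position: 1/2; 1/2 + p/6; 1/2 + [1−(1−p)²]/6; 1/2 + [1−(1−p)³]/6 + p³/3.

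| Collectors | p | Certain = p²/3 | Of 144 | Correct guesses by position | Mean |
|---|---|---|---|---|---|
| 1 | 1 | 33.3% | 48 | .500, .667, .667, 1.000 | 70.8% |
| 2 | 1/2 | 8.3% | 12 | .500, .583, .625, .688 | 59.9% |
| 3 | 1/3 | 3.7% | 5.3 | .500, .556, .593, .630 | 56.9% |

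Under full concealment the guess rate is 50% and nothing is certain. Collectors who share information move back towards the first row.

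**Varying block sizes.** With sizes drawn at random from 4, 6 and 8 and kept hidden, a simulation of 4,000 sequences of 24 gives an observer of every assignment about 2% certain and about 67% guessed correctly. Certainty nearly disappears, but the guess rate hardly moves from 71%.

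**The case against.** The plan has real safeguards. Randomization follows consent and a completed baseline, the envelopes stay out of the field, and the project director releases the assignments. These protect the current father's assignment, and that credit stands. The remaining weakness is inference from previous assignments; this is not open allocation.

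Several links are inferred. The plan does not say that each text is sent before the next father is seen, that the texted collector obtains consent, or that field staff knew the block size. Its three recruiters are not said to receive the texts. Father-by-father release is nevertheless the natural reading, because randomization follows each father's baseline. Tying the collector's blindness to consent and enrolment suggests a part in both. The 33% figure needs one collector who sees everything, so the range must be quoted.

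Two stronger readings are tempting, and the documents do not support them.

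- **That outcome collectors were unmasked.** The same role title is used and no masking is described, but nobody is named as taking the 12- and 24-week measures. Fathers are not said to be interviewed, and mothers' postal or online answers need no collector. The supportable statement is that masking is not described and appears absent.
- **That fathers dropped out before the first session because they knew their arm.** When fathers were told is not stated and no such withdrawal is reported. The plan specifies intent-to-treat analysis, multiple imputation and an attrition check. Batch release would also tell fathers their arm before the first session.

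**Conclusion.** The point holds as a weakness in concealment. Small fixed blocks, ordered release and disclosure to a role that appears to share in enrolment allow some later assignments to be predicted. The size is about 4% to 33% known with certainty and 57% to 71% guessed correctly, against 50% under concealment, for three collectors who do not share information down to one who sees all. These are upper bounds: they assume knowledge of block size and position, father-by-father release and a collector who takes part in enrolment. More than three separate collectors would lower them further.

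The lack of any description of follow-up masking matters for measures given in person or by phone, and less for answers by post or online. Nothing here shows that bias occurred, and the sample size calculation is unaffected. The change is worth making because it is cheap; confidence is medium because of the inferred links.

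**What to change.** **Main change.** Release each wave's assignments in one batch after that wave's last baseline, and start every wave with a new block. Both groups begin only when the 12-week recruitment closes, so the plan gives no operational reason to release them sooner. With no enrolment decision left in the wave, prediction has nothing to act on. Send the assignments to the group leaders and the fathers, not to the data collectors, and state that follow-up collectors are not told the arm.

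**If release must stay sequential.** Still redirect the texts away from enrolling and data-collecting staff, and use varying block sizes that are not disclosed to them. Varying the sizes alone is only a partial remedy, as the 67% guess rate shows.

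**Cost.** A different release date and recipient; no added staff or visits. The downside is that early enrollees learn their group and meeting night nearer the start, in some cases after most of the 12 weeks.

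**If enrolment has already closed**, as the mostly past-tense text suggests, report who received assignments and when, how many collectors shared a sequence, whether they knew the block size, and whether follow-up collectors knew the arm. Compare baseline characteristics by arm at the predictable positions: every fourth place, and the third place where the first two match. With 144 assignments about 48 such places are expected, roughly 24 per arm, so finding no difference would not exclude selection.

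### Non-significant baseline tests cannot show that the randomised arms are comparable, and the Hypothesis 1 and 3a models do not adjust for the imbalance that is actually observed

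*Combined protocol and SAP*

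**What the plan says.** Under Data Analysis, after the descriptive statistics, the plan gives this check: "one-way ANOVAs and chi-square analysis on the demographic and baseline research measures were performed between the intervention and control groups to determine that they". The sentence runs over a page break and ends by naming comparability of the arms as the aim. The level comes from the same section: "A two-tailed 0.05 significance level was used for all statistical tests except where noted below". No exception is noted for the baseline tests. The section gives no imbalance threshold, standardised difference or multiplicity allowance, and it does not say what follows from either result.

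The arms are formed by chance. Overall Study Design says "This study used a block randomization procedure to facilitate equitable distribution of fathers into the BBTF and FLP conditions" and "Each block was constructed with an equal number of BBTF and FLP assignments". Sample Recruitment places randomisation after consent and baseline measurement.

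For Hypothesis 1, "The basic design for these analyses was a 2x3 design with three assessment time points" crossed with the two conditions, and the treatment effect is the interaction. Baseline is one of the three time points and no covariate is listed. Hypothesis 3a is analysed in the same way with child outcomes. The mediation regressions described under Hypothesis 2, and taken over for Hypothesis 3b, do condition on the earlier value of the outcome.

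**The concern.** A significance test asks whether a difference could be due to chance. Between properly randomised arms the answer is known beforehand: it is. A significant result is then a false alarm, and a non-significant one says only that the observed difference is below a limit set by the sample size. How far an imbalance matters depends on its size and on how strongly the variable predicts the outcome, and a p-value measures neither.

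Two things are at stake. First, the report may call the arms comparable while an outcome's baseline differs by an amount that is large next to the planned effect, or may cast doubt on a valid randomisation because one of many tests came out significant. Second, the models that test the treatment effect make no adjustment for the imbalance observed. Because baseline enters as a repeated level, a chance difference there pulls the change contrast in the opposite direction.

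**Working it through.** **Inputs from the documents.** Power Analysis: "a one-tailed alpha of .05, and a sample size of 144 participants (72 per group), we obtained a power of .80 for this design", with a planning effect of d = .42; after an allowance for 20% dropout, 180 fathers are to be randomised, 90 in each arm. Data Analysis: two-tailed .05. Named outcomes: six under Hypothesis 1 (psychological well-being, parenting competence, father-mother relationship quality, material support, in-kind support, father-child interaction) and three under Hypothesis 3a (behavioural, emotional, social), nine in all.

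**Assumptions.** Baseline to follow-up correlation rho of .5 to .7; equal variances over time; correlation between outcomes of 0 to .5; normal approximation, one follow-up visit and complete data for the conditional rates. The documents give none of these.

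**1. The plan's own figure.** One-sided power with 72 per group is Φ(.42 × √(72/2) − 1.645) = Φ(0.875) = .81, against the stated .80. Allowing for dropout, 144/0.80 = 180. Both reproduce. Baseline data precede randomisation and dropout, so 90 per arm is the relevant number below.

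**2. Largest observed difference that is non-significant.** In SD units this is t(.975, 2n − 2) × √(2/n). With n = 90: 1.973 × 0.1491 = 0.294, and 0.294/.42 = 70%. For a binary variable near 50% it is 1.96 × √(.5/90), about 14.6 percentage points. Mother-reported measures would have a wider limit if some mothers did not take part; the documents do not allow a figure.

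**3. At least one false flag under sound randomisation.** For nine independent tests: 1 − .95^9 = .37. With equal correlations among the nine, simulation gives .33 at .3 and .27 at .5. The range is therefore about 27% to 37%. Mothers' reports and demographic variables add further tests, but the demographic variables are not listed.

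**4. What a baseline imbalance does to the change contrast.** Given an observed baseline difference D and no treatment effect, the expected follow-up difference is rho × D, so the expected change contrast is −(1 − rho)D. The first Helmert contrast, baseline against the mean of both follow-ups, has an expected shift of the same size if both correlations equal rho. At D = 0.294 the shift is 0.15 SD for rho = .5 and 0.09 SD for rho = .7.

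**5. Conditional rejection rate of a two-tailed .05 change comparison with no effect.** The contrast has conditional variance (1 − rho²)(2/n) and is tested against a standard error of √(2(1 − rho)(2/n)). Take D = 0.28 and rho = .6 with n = 90:

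- mean −0.112, conditional SD √(.64 × 2/90) = 0.119, critical value 1.96 × √(.8 × 2/90) = 0.261
- lower tail Φ((−0.261 + 0.112)/0.119) = .105, upper tail .001, total about 11%

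| D | rejection rate, rho = .7 to .5 |
|---|---|
| 0.28 | 9% to 12% |
| 0.20 | 6% to 7% |
| 0.15 | about 5% |
| averaged over every D that is non-significant | 4.6% to 4.3% |
| averaged over all randomisations | 5% |

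The first row is the edge of the range. The chance that a given variable falls between 0.28 and 0.294 in absolute value is about 1.2%.

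**6. Gain from adjustment.** For one follow-up visit the variance is proportional to 1 − rho² with the baseline value as a covariate and to 2(1 − rho) for change from baseline. The ratio is (1 + rho)/2: .75 at rho = .5 and .85 at rho = .7, a cut of 25% and 15%.

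**The case against.** The strongest case on the other side is that the tests do nothing. The plan states a purpose but writes no accept or reject criterion, and no covariate, exclusion or model depends on the outcome of a test. Deleting them would alter no estimate and no p-value, and the plan obtains descriptive statistics anyway. All of that stands.

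It also stands that regression to the mean arises from the repeated measures model and not from the baseline tests: it would be the same if no test were run. Nor does the plan ignore baseline. The interaction is a comparison of change, which removes part of a stable offset, and the mediation regressions condition on it.

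A reader might infer that clearing the arms as comparable inflates the trial's false-positive rate, perhaps to 11%. The documents do not support that. The 11% applies to one visit, one change score and an imbalance just below the limit; averaged over imbalances that are non-significant, the rate is slightly below 5%. Nearly all the extra rejections go against the arm with the higher baseline, so they are as likely to suggest false harm as false benefit. The planned procedure also has two follow-ups and examines univariate results only after a multivariate rejection, so none of these conditional rates is its error rate.

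What the objection does not remove is the invalid inference in the stated purpose, or the lack of adjustment in the models that test the treatment effect.

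**Conclusion.** The point holds in a limited form. Establishing comparability by between-arm tests is not a valid inference in a randomised trial: at 90 per arm it cannot separate balance from an observed difference of 0.29 SD, and for the nine named outcomes it yields at least one false alarm in about 27% to 37% of sound randomisations. These figures use the plan's own sample size and level; the lower end of the second range rests on an assumed correlation of .5 between outcomes.

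The practical consequence lies in the Hypothesis 1 and 3a models. Without the baseline value as a covariate, the contrast is biased given the imbalance observed and less precise than it could be. The case is about conditional bias and precision, since type I error over all randomisations stays at 5%. The documents do not show that the randomisation was faulty, that the plan acts on a test result, or that any conclusion was wrong. The change should be made, but the trial's validity does not hang on it.

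**What to change.** 1. In Data Analysis, drop the between-arm ANOVAs and chi-square tests as evidence of comparability. Report means, SDs and percentages by arm, with standardised differences and no p-values, and base no claim of comparability on non-significance.
2. For Hypotheses 1 and 3a, analyse the 12- and 24-week values as the outcomes, with the outcome's own baseline value as a covariate. Removing the tests without this step changes no result.
3. Add a short fixed list of prognostic variables already collected at baseline, included whatever balance is observed. State that no covariate enters or leaves because of a baseline test.

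The cost is a few degrees of freedom and some re-specification of the model, since baseline moves from a level of the time factor to a covariate and the Helmert contrasts must be restated. No new data are needed. The plan is written largely in the past tense; if outcome data have already been seen, label the adjusted analysis post hoc and show it beside the planned one. The first step can be taken in either case.
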